	4.9.2 Requirements for Informed Consent	
4.10	Subject Data Confidentiality	19
5	Risks and Benefits	
6	Registry Management	20
6.1	Procedures to Amend the Registry Protocol	20
6.2	Sponsor Responsibilities	20
6.3	Role of the Sponsor Representatives	20
6.4	Investigators	21

ReActiv8-C Post-Market Surveillance Registry

	6.4.1	Record Keeping	21
6.5	Public	Record Keepingations	21
6.6	Regist	ry Monitoring	22
6.7		ry Completion	
6.8		nsion or Premature Termination of the Registry	
6.9		and Address of the Sponsor	
6.10		nents of Compliance	
Appe	endix 1	: Acronyms and Definitions	23
Appe	endix 2.	: Bibliography	24
Tab	le of	Tables	
Table	1: Safe	ty Reporting Definitions	11
Table	2: Adve	erse Event Relatedness Categories	12
Table	3: Data	Collection Schedule	18

Registry Summary

Registry Purpose	To gather data on the long-term safety of ReActiv8 and identify any residual risks by reporting all Serious Adverse Device Effects as well as performance and health care utilization through two years post-implant.						
Indications For Use	ReActiv8 is an adjunct to medical management of Chronic Low Back Pain for relief of pain in adults who have attempted at least medical management and physical therapy.						
Registry Device	eActiv8						
Registry Design	The ReActiv8 Registry is an international, multi-center, data collection registry in Subjects who meet the CE Mark indications and are not contraindicated for ReActiv8. A minimum of 50 Subjects will be implanted at up to 25 sites. Subjects will be followed for two years post-implant, at which point they will be exited from the Registry.						
Population	A minimum of 50 Subjects will be implanted at up to 25 sites.						
Enrolment Criteria	 Inclusion Criteria Meet the Indications for ReActiv8 Willing to sign the Informed Consent for the ReActiv8-C Post-Market Surveillance Registry Age ≥ 18 years Exclusion Criteria Contraindicated for ReActiv8 						
Safety, Performance, Health Utilization Measures	 Assessment of all Serious Adverse Device Effects that occur through two years post-implant. Performance Change in average low back pain from baseline to follow-up visits (NRS) Change in Oswestry Disability Index from baseline to follow-up visits (ODI) Change in EQ-5D from baseline to follow-up visits (EQ-5D) Assessment of Percent Pain Relief at follow-up visits (PPR) Assessment of Subject Global Impression of Change at follow-up visits (SGIC) Assessment of Patient Treatment Satisfaction at follow-up visits (TSQ) Health Care Utilization Change in work status from baseline to follow-up visits Change in use of opioids from baseline to follow-up visits Assessment of Health Care Utilization (office visits, hospital visits, imaging and diagnostics and other pain management treatments) at follow-up visits 						
Study Visit Schedule	 Visit 1: Baseline visit Visit 2: Activation visit: Approximately 14 days post-surgery Visit 3: 3 month visit: 90±30 days post-activation Visit 4: 6 month visit: 180±30 days post-activation Visit 5: 1 year visit: 1 year±60 days post-activation Visit 6: 2 year visit: 2 year±60 days post-activation 						

2. Background

Mainstay Medical has developed an implantable medical device designed as therapy for people with chronic low back pain (CLBP). The device, called ReActiv8®, consists of two implantable leads with four electrodes each, configured to deliver electrical stimulation to the medial branch of the dorsal ramus nerves as they cross the transverse process at L3 to elicit bilateral contraction of the lumbar multifidus muscles (MF). The leads are coupled to a battery powered implantable pulse generator (IPG) which is activated by an external Activator and is programmed using Application Software provided on a laptop computer. Several accessories are included as part of the system, for example to facilitate the surgical procedure.

The therapy delivered by the ReActiv8 was explored with a European Feasibility Study in 2011 to 2013 using "off the shelf" general purpose neurostimulation devices from other manufacturers, and results have been published.¹

ReActiv8 was investigated under an ongoing clinical trial at nine sites in Australia and Europe (ReActiv8-A). The data from the first 47 Subjects implanted with ReActiv8 in this trial served as the basis for CE Marking on 24-May-2016. A summary of the ReActiv8-A Trial can be found at http://clinicaltrials.gov/show/NCT01985230.

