4.1. Objective

To gather data on the long-term safety of ReActiv8 and identify any residual risks by reporting all Serious Adverse Device Effects as well as performance and health care utilization through two years post-implant.

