4.2. Overview

The ReActiv8 Registry is an international, multi-center, data collection registry in Subjects who meet the CE Mark indications and are not contraindicated for ReActiv8. A minimum of 50 Subjects will be implanted at up to 25 sites. Subjects will be followed for two years postimplant, at which time they will be exited from the Registry. Subjects may decide to be enrolled in the registry before or after implant so that information on the performance of the system can be collected.

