4.4.4. Reporting by the Sponsor

All SADEs reported in the Registry will be reported to the Notified Body on an annual basis.

SADEs that meet the criteria of an Incident per MEDDEV 2.12/1 (Revision 8) shall be reported as part of Vigilance reporting to the relevant competent authority and to the Notified Body. Vigilance reportable events will be reviewed for reporting requirements in other applicable geographies outside of the European Union.

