4.7. Data Collection Schedule

The data for the registry will be collected according to the following schedule:

Visit 1: Baseline visit

Visit 2: Activation visit (approximately 14 days post-surgery)

Visit 3: 90±30 days Post-Activation

Visit 4: 180±30 days Post-Activation

Visit 5: 1 year±60 days Post-Activation

Visit 6: 2 years ±60 days Post Activation

The above mentioned visits are part of the standard of care for patients with this type of treatment. The given time windows are advisable and data collection outside these windows will not be seen as a protocol deviation.

Any unscheduled visits will be recorded as stated in Table 3 and in section 4.7.6.

Note that data collection of all performance measures shall be done as the first thing in the follow up visit, prior to any other procedures.

Note that once a Subject has consented to participate in the Registry Adverse Events will be collected at each visit.

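### Does an exit dated two years from implant shut out a final visit dated two years from activation?

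*Protocol*

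**What the plan says.** Two time origins are in use.

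**From implant.** The Registry Summary says "Subjects will be followed for two years post-implant, at which point they will be exited from the Registry", and section 4.2 gives the same end of follow-up, "at which time they will be exited from the Registry". The Summary's safety measure is "Assessment of all Serious Adverse Device Effects that occur through two years post-implant". The objective in section 4.1 extends the same horizon to "performance and health care utilization through two years post-implant".

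**From activation.** The Summary's visit schedule has "Visit 6: 2 year visit: 2 year±60 days post-activation", and section 4.7 has "Visit 6: 2 years ±60 days Post Activation". Section 4.7.5 and the column heading of Table 3 agree.

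Section 4.7.2 links the two: activation is planned for about 14 days after implant surgery. It may be postponed if the Subject cannot use the device at that time, and no upper limit is given. Section 4.7 adds: "The given time windows are advisable and data collection outside these windows will not be seen as a protocol deviation". No sentence says that exit takes place at Visit 6.

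**The concern.** Read literally, a Subject has left the registry before the target date of the last scheduled visit, and this happens in the planned case. Any activation later than the day of implant puts the Visit 6 target after the stated exit, and a postponed activation widens the gap.

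Visit 6 matters. It is the only scheduled source of two-year NRS, ODI, EQ-5D, PPR, SGIC and TSQ data. It is also the second of only two follow-up entries on the Health Care Utilization row of Table 3.

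There is a safety side as well. Section 4.4.4 says "All SADEs reported in the Registry will be reported to the Notified Body on an annual basis". If a Subject has formally exited, one could ask whether an event occurring between exit and Visit 6 belongs in that report. For a registry whose stated purpose is long-term safety, the end of observation should be clear.

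**Working it through.** **The plan's own figure.** The only calculated figure in the Protocol is in section 4.8: 50 Subjects give 80% power to see at least one event at a population rate of 3.2%. It reproduces: 1 − (1 − 0.032)^50 = 1 − 0.968^50 = 0.803. Its inputs are a number of Subjects and a rate. The implant or activation date does not enter, so the choice of clock leaves it unchanged.

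**Inputs for the dates.**
- Exit: two years after implant (Registry Summary, section 4.2), or 2 × 365 = day 730.
- Visit 6: two years ± 60 days after activation (Summary, sections 4.7 and 4.7.5, Table 3).
- Lag L from implant to activation: about 14 days (section 4.7.2). Longer lags are possible, but the Protocol gives no distribution for them.

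**Formulas, in days after implant.**
- Visit 6 target = L + 730.
- Visit 6 window = L + 670 to L + 790.
- Target minus exit = L. This also holds if two years are counted as 731 days.
- Day 730 lies in the window when L + 670 ≤ 730, that is, when L ≤ 60.

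**Results.**

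| Lag L | Target | Window | Target minus exit | Day 730 in window? |
|---|---|---|---|---|
| 14 (planned) | 744 | 684 to 804 | 14 | yes |
| 30 (assumed) | 760 | 700 to 820 | 30 | yes |
| 60 (assumed) | 790 | 730 to 850 | 60 | yes, first day |
| 61 (assumed) | 791 | 731 to 851 | 61 | no |

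At the planned lag a visit on day 730 falls 730 − 14 = 716 days after activation, 14 days ahead of target and within the 60 days allowed. Both rules can then be met on the same day. The window and the exit separate completely only at a lag of 61 days or more, which is 61 − 14 = 47 days beyond plan. Even there, section 4.7 does not treat data collected outside the window as a deviation.

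**Safety horizon.** The Summary's measure is framed by when events occur. An event with onset by day 730 that is entered at a Visit 6 on day 744 is within the horizon by definition. Section 4.4.1 collects all adverse events, section 4.4.3 has the investigator report all of them, section 4.7 collects them at each visit, and Table 3 ticks them at Visit 6. The only events in doubt are those with onset after day 730 and before a later Visit 6. That span is 744 − 730 = 14 days for a target-date visit at the planned lag. Events that meet the Incident criteria also have the vigilance route in section 4.4.4.

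**The case for a change.** The best argument for a change is that neither timing of Visit 6 is fully covered. A visit after day 730 follows the stated exit. A visit before it leaves the end of the safety horizon without a scheduled contact: at the planned lag, a visit on the first day of the window leaves 730 − 684 = 46 days. Advisory windows move the visit but do not move the exit. Exit and visit timing are protocol content, so a statistical analysis plan cannot be relied on to settle them, and a sentence of clarification would cost little.

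Part of this stands. The anchors do differ, no passage reconciles them, and section 4.7 does not alter the exit sentence. The practical consequence does not follow. The 46 days arise from holding the visit at the earliest permitted date, and a window around any anchor has that property. Investigator reporting under section 4.4.3 is not tied to a visit. As for exit, every statement of when Visit 6 takes place uses activation, while the post-implant wording sits in the purpose, design, objective and overview text, where it reads naturally as a rounded description of a two-year registry. A site is unlikely to discharge a Subject about two weeks before a final visit that the same document schedules. Changing the exit sentence alone would also leave the performance and utilization horizon in section 4.1 on the implant clock, so the text would still not be fully aligned.

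**Conclusion.** This is a minor inconsistency of wording, and no change to the plan follows. Its size on the planned schedule is 14 days in 730, or 14/730 = 1.9%. A Visit 6 that is held loses no data, and one held on day 730 at the planned lag satisfies both statements. Analysts can label the two-year results by Visit 6 and count serious adverse device effects by onset date from implant, listing any later ones separately. The 80% figure in section 4.8 is unaffected.

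The conclusion rests on three assumptions: sites follow the visit schedule in section 4.7 and do not discharge Subjects on day 730; onset dates of events are recorded; and long postponements of activation are not the norm. The Protocol gives no distribution of activation lags, so no share of Subjects can be stated. A longer lag would widen the gap day for day, but the visit would still be a two-year visit on the clock that every entry in the schedule uses.

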2.1. Chronic Low Back Pain

Low back pain is usually defined as pain and discomfort, localized below the costal margin and above the inferior gluteal fold, with or without referred leg pain. ^{2,3} Chronic Low Back Pain (CLBP) is usually defined as back pain for at least 3 months. The NIH Task Force on Research Standards for Chronic Low Back Pain recommended that Chronic Low Back Pain be defined as a back pain problem that has persisted for at least 3 months and has resulted in pain on at least half the days in the past 6 months.

Chronic low back pain is a major health problem, and the World Health Organization reports that "Low back pain is the most prevalent of musculoskeletal conditions; it affects nearly everyone at some point in time and about 4–33% of the population at any given point." There are many publications on the epidemiology⁶ of back pain including prevalence, 7,8,9 natural history, demographics, and country by country variability.

People with acute low back pain and associated disability usually improve rapidly within weeks, but pain and disability typically continue, and recurrences are common. Although most episodes of acute back pain resolve within 3 months, recovery after 12 weeks is slow and uncertain. Fewer than half of those individuals disabled for longer than 6 months return to work and, after 2 years of absence from work, the return-to-work rate is close to zero. It is many chronic conditions, the costs are driven by the small proportion of the population who have been sick for the longest period – for back pain, patients with disability >1 year account for 5% of cases, but 65% of costs.

Although there has been a lot of attention and investment applied to surgical treatments for low back pain, only approximately 20% of patients are suitable surgical candidates. ¹⁴ The remaining patients are sometimes referred to as having "non-specific low back pain" (NSLBP) or "axial low back pain" (ALBP). There are European clinical practice guidelines for chronic NSLBP² and UK guidelines for management of patients with persistent CLBP (published by the National Institute for Clinical Excellence - NICE). ¹⁵ US guidelines for acute and chronic low back pain are similar to the European guidelines. ¹⁶

Exercise therapy is frequently prescribed for NSLBP, but the effectiveness of exercise therapy for *acute* back pain is negligible.¹⁷ Systematic reviews of the literature^{18,19} concerning therapies for *chronic* low back pain show that exercise is generally ineffective,

other than certain types of exercise therapy which can be effective in a small subset of patients.

Many non-invasive therapies have been tried with modest or no success, and several reviews are available. 20 Therapies include lumbar extensor strengthening exercises: 21 watchful waiting (i.e., no therapy),22 traction therapy,23 the McKenzie Method of exercise therapy,²⁴ various types of energy application including ultrasound, TENS,²⁵ osteopathic therapy, ²⁶ and thermotherapy, ²⁷ and lumbar stabilization exercises. ²⁸

"Usual care" or "conventional medical management" for CLBP usually consists of coping mechanisms for pain, and pain medications (often opioids), which are often increased during the episodic flare-ups of pain.

2.2. ReActiv8

Arthrogenic muscle inhibition (AMI)²⁹ is the physiological mechanism by which pain in a skeletal joint disrupts the motor control to the muscles that stabilize the joint - often observed in the quadriceps post knee surgery. A similar mechanism underlies some types of chronic low back pain, with disruption to the motor control of the key stabilizing muscles the lumbar multifidus. Evidence includes diminished EMG activity in back pain patients³⁰ and delayed reflex response of the MF to perturbations.³¹ Pain alters the magnitude of activation of deep MF during certain types of activity.³² Ultrasound imaging evidence of reduced neural drive in back pain patients includes diminished cross sectional area with contraction,33 reduced ability to cause a muscle thickness change on command, 34 and altered contraction patterns with changes in posture.35

Published studies show that subject initiated contraction of the lumbar multifidus with ultrasound guided biofeedback motor control physical therapy exercises can lead to improvements in back pain, but this approach has not been adopted due to practical challenges, economic difficulties, and patient compliance issues. The mechanism of action is believed to be restoration of motor control of the lumbar multifidus, thereby leading to rehabilitation of the muscle, improved spine stability and reduction in back pain.

Electrical stimulation to restore motor control has been successfully used with other skeletal muscles. In particular, stimulation via superficial (skin) electrodes over the motor point of the quadriceps can restore neural drive and allow rehabilitation of the muscle in patients following total knee arthroplasty³⁶ or other surgical procedures.^{37,38} Painful knee osteoarthritis can be treated without surgery but may also lead to pain mediated inhibition of neural drive to the quadriceps, which can be treated effectively with electrical stimulation.³⁹

ReActiv8 has been designed to incorporate the principles of these prior approaches. Electrical stimulation of the medial branch of the dorsal ramus nerve that innervates the lumbar multifidus is delivered episodically (in a stimulation session of 10 seconds on 20 seconds off, for 30 minutes, twice per day).

3. ReActiv8 Therapy

3.1. Summary of ReActiv8

ReActiv8 is a CE Marked implantable electrical stimulation system consisting of the following components:

- 1. Implantable Pulse Generator (IPG) (pre-loaded with IPG Firmware Code and packaged with a Torque Wrench to aid in implant procedure)
- 2. Percutaneous Leads (with Stylet and Suture Sleeves)
- 3. Application Software
- 4. Programmer Wand
- 5. Activator (pre-loaded with Activator Firmware Code)
- 6. Magnet
- 7. Tunneler

The ReActiv8 Programmer Wand and Application Software are provided with a commercially available laptop computer and AC adapter. Commercially available surgical tools such as a 7Fr Introducer Kit is used at implant and is not part of ReActiv8.

ReActiv8 delivers stimulation via electrodes placed adjacent to the medial branch of the dorsal ramus nerve at the preferred location as it crosses the L3 transverse process. The electrodes are located at the distal end of a Stimulation Lead that is connected to an implantable pulse generator (IPG) placed in a surgical pocket typically above the buttocks (in a place similar to that used in Spinal Cord Stimulation implants). Two leads are placed (one each left and right side) and connected to the IPG. The IPG is externally programmable via Application Software stored on a laptop computer. Stimulation is manually initiated by an external device (Activator) and can be stopped with the Activator or Magnet.

The leads incorporate a fixation mechanism that consists of two sets of 3 point tines – one set facing forward and one set facing backwards. The tines are positioned to lie on either side of the intertransversarii lateralis, thus reducing the risk of lead migration by either advancement or retraction. The lead body is a polyurethane tube containing the lead conductor, incorporating a lumen to allow passage of a stylet. Refer to the Implant and Programming Manual for more detail on device specifications and operation.

3.1.1. Implantable Components of ReActiv8

The ReActiv8 IPG, and the two sizes of leads (45 cm and 65 cm), plus suture sleeves, are designed for permanent implant. The implantable components of ReActiv8 are supplied sterile, and are intended for single use only.

- Model 5100 ReActv8 Implantable Pulse Generator ("IPG") pre-loaded with Firmware Code
- Model 8000-45 ReActiv8 Percutaneous Lead, 45 cm length ("Lead")
- Model 8000-65 ReActiv8 Percutaneous Lead, 65 cm length ("Lead")
- Model 8145 ReActiv8 Percutaneous Lead, 45 cm length ("Lead")
- Model 8165 ReActiv8 Percutaneous Lead, 65 cm length ("Lead")

3.1.2. Non-Implantable Components of ReActiv8

The Torque Wrench and Stylet are provided to facilitate implantation of the IPG and leads. The Application Software and Programmer Wand are used with a laptop computer to communicate with the IPG in order to program the IPG operational mode and settings, read history data from the IPG, and obtain IPG and lead status information. The Activator is used

to initiate and/or suspend stimulation. The Magnet is used to enter Magnet Mode (with Magnet Mode operation determined by the programmed parameters of the IPG).

The non-implantable components of the ReActiv8 system are:

- Model 7000 ReActiv8 Activator ("Activator") with Firmware Code
- Model 4000 ReActiv8 Magnet ("Magnet")
- Model 5500 Torque Wrench ("Torque Wrench")
- Version 1.0.1.6 (English) and 1.0.1.9 (Multilanguage) Application Software
- Model 6000 Programmer Wand ("Wand")
- Model TUN1 Mainstay Tunneler ("Tunneler")

The ReActiv8 Programmer Wand and Application Software are provided with a commercially available laptop computer and AC adapter.

3.2. Indications for Use

ReActiv8 is an adjunct to medical management of Chronic Low Back Pain for relief of pain in adults who have attempted at least medical management and physical therapy.

3.3. Contraindications

ReActiv8 is contraindicated for patients who are:

- Unable to operate the system
- Unsuitable for ReActiv8 implant surgery

3.4. Surgical Implantation and Device Activation

The surgical implantation procedure, device programming, and use by the Subject are per the Implant and Programming Manual and the User Manual.

In normal use, following implantation and a suitable recovery period, the IPG is programmed to deliver stimulation that elicits smooth contraction of the lumbar multifidus. Typical parameters are 0.5 mA, 200 μ s, 20 Hz, with a duty cycle of 10 seconds on and 20 seconds off, delivered for a Session of 30 minutes.

To start a Session, it is recommended that the Subject is positioned comfortably prone or lying on the side. The Subject initiates delivery of electrical stimulation with the Activator, which can also be used to stop stimulation (e.g.: in case of interruption). Two sessions of stimulation, each of 30 minutes, are delivered each day (e.g. morning and evening).

3.5. Physician and Health Care Personnel Training

All physicians who will implant any portion of the ReActiv8 system in the ReActiv8 Registry must have participated in product training. The Sponsor will document completion of training for each implanting physician.

All physicians and other health care personnel who will interact with the programming system will receive training from the Sponsor, which includes lectures and use of a programming system with a simulator. This training will also include interaction with the Activator and Magnet handled by the Subject.

Registry Design 4.

